## **9.6 Safety Oversight**

Safety oversight will be under the direction of a DSMB composed of [name], an epidemiologist, a biostatistician and one or more clinical researchers. The DSMB will review AEs every 6 months whereas the medical monitor will review AEs in real time and make decisions as to each participant's continuation in the trial. The PI will review AEs weekly with research team and may request additional review by Co-I on a case-by-case basis. The medical monitor will also be present at weekly meetings in order to discuss/explain any event(s) that may occur.

Every 6 months DSMB will review blinded AE reports. If there is reason to view unblinded information, the DSMB will directly receive the list of participants' identification numbers from a [name] Lab member, not otherwise associated with this clinical trial. Participant identification number will be displayed in a table according to the three arms of the study; however the specific treatment of that arm will not be disclosed. This will allow the DSMB to compare the three treatment groups.

Reasons for stopping the study and asking for further investigation include; decrease in cognitive abilities based on baseline and end of study data (>25% decrease in scores in 2/10 of the first participants or 20% of participants overall.). In addition, as mentioned above, if a seizure occurs during a study visit, the clinical trial will be temporarily be placed on hold for further investigation.

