## PROTOCOL SUMMARY

Title:	Targeting Auditory Hallucinations with Alternating Current Stimulation
Précis:	
The purpose to determine the efficacy of transcranial alternating current stimulation, tACS, versus sham stimulation (with tDCS versus sham as a positive control for assay sensitivity) for the treatment of medication-refractory auditory hallucinations in patients with schizophrenia. We will recruit 48 males and females diagnosed with schizophrenia or schizo-affective disorder. Eligible participants will have 5, twice-daily (one week Monday through Friday), 20 minute stimulation sessions. Stimulation will be at least 3 hours apart. Participants will be randomly assigned to one of three groups; sham stimulation, 10 Hz (alpha) tACS or 2 mA tDCS. Participation will involve 1 to 8 visits. At the initial session, informed consent will be obtained and subjects will be screened for eligibility. Eligible participants will then be scheduled for their, twice-daily stimulation sessions which will include daily assessment of stimulation side-effects. Clinical assessments will be performed at baseline, 1, 2 and 4 weeks using the Auditory Hallucinations Rating Scale (Attachment 3). Neurophysiological (EEG) and cognitive assays will be performed before and after stimulation. Please see Appendix A for a detailed schematic describing all visits and assessments.

Objectives:	
Our primary objective is to demonstrate the value of synchronization and information flow measures derived from EEG data as novel biomarkers in the treatment of medication refractory auditory hallucinations in schizophrenia with transcranial current stimulation. To reach this objective, we will test the working hypothesis that (1) baseline impairment in EEG synchronization and information flow predicts treatment success and (2) changes in these markers correlate with improvement of clinical symptom presentation as determined by the AHRS, PANSS, and BACS (Attachment 12). We will test our working hypothesis by measuring whole-head EEG data from all patients in our feasibility study (48 patients from Aim 1) before and

immediately after the five day course of stimulation and at both follow-up visits.

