### **5.4.1 Randomization Procedures**

A [name] Lab member will randomize 48 codes which will be used by the study coordinator and research assistants. These codes are directly linked to which treatment participants receive (sham, 10Hz tACS or 2 mA tDCS). This lab member will have no other responsibility in the study other than providing these randomized codes.

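### Section 9.6 gives the DSMB no way past coded arm labels, so it cannot reliably attribute a between-arm safety imbalance to active stimulation or tell a tACS concern from a tDCS concern

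*Combined protocol and SAP*

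**What the plan says.** Section 9.6 sets two levels of access.

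- Routine: "Every 6 months DSMB will review blinded AE reports".
- On cause: "If there is reason to view unblinded information, the DSMB will directly receive the list of participants' identification numbers". The list comes from a lab member with no other part in the trial. It is tabulated by arm, with this limit: "however the specific treatment of that arm will not be disclosed".

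The stated purpose of the second level follows directly: "This will allow the DSMB to compare the three treatment groups".

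The Protocol Summary defines the arms: "Participants will be randomly assigned to one of three groups; sham stimulation, 10 Hz (alpha) tACS or 2 mA tDCS". It gives the tDCS arm a separate role, "with tDCS versus sham as a positive control for assay sensitivity". Table 1 allots 16 participants to each arm. Section 5.4.1 has a lab member prepare 48 codes tied to treatment, so the key exists and someone outside trial conduct holds it.

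**The concern.** Section 9.6 calls the second level unblinded, but it only adds grouping. The three groups are not interchangeable: one is the control and two are active, with different purposes. The question behind a by-arm adverse event table is whether either active arm does worse than sham, and if so which one. Three anonymous columns show that the arms differ but not what the difference means.

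This matters because several harms the protocol anticipates can also arise without stimulation: worsening symptoms (2.3.1), a rise in PANSS (9.1) and a fall in cognitive scores (9.6). For such events, case-by-case causality is weak evidence and the comparison with sham carries much of the weight. Other features of the table do not reveal the control either. Arm sizes are equal, and section 4 describes an active sham meant to imitate the skin sensations of tACS, so local side effects may not mark it.

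**Working it through.** The plan states no figure on this point. The check is of the text, followed by an illustration on assumed counts and rates, because the documents give no adverse event rates.

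**1. Is there a further step anywhere?** Four places could bear on it.

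| Place | Content | Gives the DSMB arm identity? |
|---|---|---|
| 9.6 | Coded three-arm list on cause | No; identity is withheld and no exception is stated |
| Appendix D, item 7a | SAE form asks which intervention was received | No; a form completed by staff, with no unblinding procedure |
| Appendix K | Enrollment log has a column for treatment arm | No; no route to the DSMB |
| Appendix P | Off-study form asks whether treatment was unblinded | No; a tick box only |

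**2. Which written safety actions need arm identity?**

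- Seizures (9.5): counted study-wide; not needed.
- Cognitive decline (9.6): counted over the first 10 participants or over all participants; not needed.
- Unexpected events (9.2.4): recruitment and procedures stop for everyone; not needed.
- PANSS rise above 25% (9.1): individual referral and an AE report; not needed.
- Comparison of the three groups (9.6): needed to say whether an imbalance lies with active stimulation, and with which form of it.

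**3. One coded table, two readings.** This is a hypothetical at full enrolment, 16 per arm, with events in 5, 1 and 1 participants.

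- If the high arm is active: active (5 + 1)/32 = 18.75%, sham 1/16 = 6.25%, difference +12.5 percentage points. Two-sided Fisher p = 0.40 pooled; the high arm alone against sham, 5/16 v 1/16, gives p = 0.17.
- If the high arm is sham: active (1 + 1)/32 = 6.25%, sham 5/16 = 31.25%, difference -25 percentage points. Fisher p = 0.03.

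The sign depends on a label the DSMB does not have. The counts are invented, so the p-values are evidence of nothing about this trial. The example shows only that the direction is ambiguous.

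**4. How often would sham look worst?** With independent binomial counts and n = 16 per arm, the probability of each outcome is the sum of Bin(s; 16, p_sham) x Bin(a; 16, p_1) x Bin(b; 16, p_2) over all (s, a, b) that satisfy it. The rates are assumptions.

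| Sham / active 1 / active 2 | Sham alone highest | Sham ties for highest | An active arm higher than sham |
|---|---|---|---|
| 10% / 10% / 10% | 0.234 | 0.221 | 0.545 |
| 10% / 20% / 10% | 0.104 | 0.133 | 0.764 |
| 10% / 30% / 10% | 0.035 | 0.058 | 0.907 |
| 10% / 30% / 30% | 0.009 | 0.021 | 0.970 |

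The ambiguity is substantial when the arms do not differ and shrinks as a true active-arm excess grows. No row helps to tell tACS from tDCS: exchanging the two active labels leaves the coded table unchanged.

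**The case against.** The case for leaving 9.6 alone is that masking a DSMB by coded arms is a deliberate choice in a 48-person pilot with five days of treatment, and no written stopping rule fails because of it. Step 2 bears that out, and the medical monitor decides on individual continuation as events occur. A coded imbalance can also prompt an inquiry, and an excess in two of three arms would hint at which are active. All of this stands, and it limits the concern to the by-arm comparison.

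The timing argument also has force. With even accrual over 2 years and reviews every 6 months, 48/4 = 12 participants enter per interval, so the DSMB would see about 4, 8 and 12 per arm at months 6, 12 and 18. With 16 per arm, little stimulation would remain to be affected. Knowing the labels would also not establish harm from counts this small.

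A reader might infer three stronger things that the documents do not support.

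- That 9.6 bars the DSMB from ever asking. The text says identity will not be disclosed and is silent on requests. In practice, though, no route is provided.
- That a coded table has no safety meaning. It has some, as above.
- That whichever arm stands out is as likely to be sham as any other. That holds only when no arm truly differs, as step 4 shows.

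What the objection does not answer is the purpose of the second level. It is reached only when there is reason to look beyond blinded reports, and it stops short of what that look is for.

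**Conclusion.** The point holds in a limited form. When the DSMB has cause to look by arm, section 9.6 gives it a coded table and nothing further. It cannot reliably attribute an imbalance to active stimulation rather than sham, and it cannot say whether a concern is about tACS or tDCS. It would be wrong to conclude that the trial's halting rules are disabled or that participants are without protection; those rules work without labels.

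The size cannot be expressed as an effect on any planned figure. Under the assumed rates, sham alone would have the most events with probability from 0.01 (both active arms at 30%, sham at 10%) to 0.23 (all arms at 10%). The conclusion itself rests on the wording of 9.6 and on the absence of any further step elsewhere, not on those rates. It is a modest weakness in safety oversight that is cheap to repair, and it should be repaired.

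**What to change.** Amend 9.6 to say, in substance: the by-arm table is first shown under coded labels; on the DSMB's request, the uninvolved lab member discloses the identity of the coded arms to the DSMB only, in closed session, and the date and reason are logged; all trial staff, the PI, the Co-I and the medical monitor remain masked.

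This keeps the present masking as the default. It costs one sentence and a log entry, since the allocation key exists and the same person already supplies the list. The downside is that DSMB members may learn the arms. Nothing in the protocol gives the DSMB a part in rating, treating or running sessions, but a member's name is removed from the public text, so the sponsor should confirm that no member has such a role.

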## **10 CLINICAL MONITORING**

The Purpose of the monitoring plan is to present the [name] Lab's approach to monitoring clinical trials. The plan facilitates compliance with good clinical practice.

- (a) The rights and well-being of human subjects are protected.
- (b) The reported trial data are accurate, complete, and verifiable from source documents.
- (c) The conduct of the trial is in compliance with the currently approved protocol/amendment(s), with GCP, and with applicable regulatory requirement(s).

This section identifies key monitoring activities and specifies the data to be reviewed over the course of a clinical trial. This is a single site, investigator initiated, clinical trial so there will be no site monitoring plan in place.

### **10.1 [name] Lab Monitoring Plan**

The latest version of the approved IRB application for this clinical trial will be followed at all times. This responsibility falls in the hands of the study coordinator and research assistants. If at any time there is a deviation from protocol, the deviation from protocol log (*Appendix O*) will be filled out. All team members will be trained on how and when to use this log. The most up to date IRB application will be on file at the Clinical Trials desk in [name]. Deviations will be sent to IRB every 4-6 weeks (if necessary).

At the end of the month clinical trials meeting with the PI, 3 randomly selected informed consent forms will be chosen. The PI will verify that (1) these forms have been filled out appropriately, and (2) the consent form process described in the SOP was followed and properly documented. Should any consent form be in violation, the research team will perform and document a complete review of all consent forms.

AE and SAE are clearly defined in the Master Protocol. Documents of AE and SAE can be found in the study binder on file at the Clinical Trials desk in [name]. It is responsibility of the study coordinator to report all events to the PI. In all weekly meetings with the PI, all AE and SAE are discussed. For our practices we have adapted the decision tree provided by UNC-CH IRB to assist with reporting of such events (*Attachment 10*).

At all weekly clinical trial team meetings, the study coordinator will chose one CRF and Source Document to asses for completion and maintenance. At weekly clinical trials meeting, with the PI will assess completeness of data on REDCap (data site). The PI has read-only access. This allows the PI to view reports that provide information on any missing data on an individual participant basis, but does not allow them to add, change or input any data.

# 11 STATISTICAL CONSIDERATIONS

## 11.1 Study Hypotheses

### 11.1.1 Primary Objective

*Null hypothesis:* There is no difference in AHRS score immediately before first stimulation session and immediately after last stimulation session between treatment groups.

*Alternative hypothesis:* There is a difference in AHRS score immediately before first stimulation session and immediately after last stimulation session between treatment groups.

### 11.1.2 Secondary Objectives

1. *Null hypothesis:* There is no difference in changes of alpha frequency power between baseline EEG and EEG at completion of stimulation between treatment groups.

*Alternative hypothesis:* There is a difference in changes of alpha frequency power between baseline EEG and EEG at completion of stimulation between treatment groups.

2. *Null hypothesis:* There is no difference in PANSS score immediately before first stimulation session and immediately after last stimulation session between treatment groups.

*Alternative hypothesis:* There is a difference in PANSS score immediately before first stimulation session and immediately after last stimulation session between treatment groups.

3. *Null hypothesis:* There is no difference in BACS score immediately before first stimulation session and immediately after last stimulation session between treatment groups.

*Alternative hypothesis:* There is a difference in BACS score immediately before first stimulation session and immediately after last stimulation session between treatment groups.

## 11.2 Sample Size Considerations

This clinical trial represents a pilot study. A pilot study is a clinical trial that is conducted to decide whether a new treatment should be tested in a large controlled trial therefore we do not calculate sample size. It is difficult to recruit a large number of patients diagnosed with schizophrenia with persistent auditory hallucinations to participate in a single site extensive study. However, based on our recent prior experience recruiting for patients with these symptoms, we expect that we can successfully recruit 48 subjects and that with 16 participants in each group that we have enough power to detect significance if there is a large effect size of twice daily tACS or tDCS on auditory hallucinations and/or the underlying biomarkers.

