Eligible participants who complete this clinical trial will have a total of 9 to 11 visits; an initial screening session, a 2nd screening session, (if needed) 2 more follow up screening sessions, 5 days of twice daily stimulation sessions, a one week and a one month follow up visit. The initial screening session will take approximately 2 hours, and each follow up screening session will take approximately 3 hours each. The first day of stimulation will take approximately 6 hours and days 2 through 4 of stimulation will take 4.5 hours each. The last day of stimulation will take about 9 hours. The one week follow up will take approximately 2.5 hours and the one month follow up will take approximately 5 hours. We estimate that total participant participation duration will be approximately 41 to 47 hours.

The primary objective is to conduct a pilot clinical trial to establish the feasibility of recruitment and implementation of the methodology and to collect preliminary efficacy data for the use of tACS by comparing AHRS scores immediately before the first stimulation session and

immediately after the last stimulation session in patients with schizophrenia or schizoaffective disorder. As a secondary objective we will assess the differential clinical effects of sham, 10 Hz and 2 mA tDCS on EEG measures of alpha oscillations.

In order to ensure symptom stability for each potential participant, there will be up to a 6 week period for the participant to achieve a stable AHRS score. The AHRS will be performed at 2 week intervals during screening. A stable score is defined as having less than or equal to 20% change. If the change between the first and second AHRS scores is less than or equal to 20%, then the participant will move on to the week of stimulation. If a stable score is not achieved at the second screening session, the participant will have two more opportunities at 2 week intervals during follow-up screening sessions to achieve a stable score. The participant will be paid for each session. If the participant does not achieve a stable score (if there remains a greater than 20% change in scores between consecutive AHRS administrations) by the end of the 6 weeks, the participant will not be eligible to continue participation.

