## 11.3 Final Analysis Plan

We will perform spectral analysis of resting state EEG before and after stimulation treatment and use a mixed ANOVA with the within subject factor session (immediately before first stimulation session and immediately after last stimulation session) and between subject factor treatment (sham, 10Hz tACS or 2 mA tDCS). Spectral analysis will be performed with multi-tapered estimation of the frequency spectrum followed by integration over the classical alpha EEG band (8-12 Hz). We will apply the same statistical analysis procedure for our primary outcome of AHRS, PANSS and BACS scores.

We will also use post-hoc paired or unpaired Student's t-test to identify the group or groups that differed. We will further control for multiple comparisons by using Bonferroni corrections.

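### Section 11.2 asserts adequate power for a large effect with no stated basis; for the between-arm AHRS test, conventional 'large' effects on the change scale give about 49% to 67%

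*Combined protocol and SAP*

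**What the plan says.** Section 11.2 describes the trial as a pilot, "conducted to decide whether a new treatment should be tested in a large controlled trial therefore we do not calculate sample size". The same paragraph then makes a positive statement of sensitivity: "with 16 participants in each group that we have enough power to detect significance if there is a large effect size", continuing "of twice daily tACS or tDCS on auditory hallucinations and/or the underlying biomarkers". The only inputs given are 16 per group and the word 'large'.

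The primary null hypothesis in section 11.1.1 is between groups: "There is no difference in AHRS score immediately before first stimulation session and immediately after last stimulation session between treatment groups". Section 11.3 will "use a mixed ANOVA with the within subject factor session" (two time points) and a three-level treatment factor, and applies this to AHRS as well as to EEG, PANSS and BACS. Paired or unpaired t-tests follow, the "t-test to identify the group or groups that differed" being their target. On multiplicity the section says "We will further control for multiple comparisons by using Bonferroni corrections", without giving the number of comparisons.

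**The concern.** A pilot may go without a sample size calculation, and nothing here asks for one. The difficulty is that the plan disclaims a calculation and then asserts its result. No section gives an alpha, a target power, a numerical effect, an SD of AHRS change or a pre/post correlation.

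The sentence matters because it is the only statement of sensitivity in the documents and there is no numerical progression rule. By section 11.2's own account, a pilot informs the decision to run a large controlled trial. Someone reading a non-significant AHRS result beside this sentence could conclude that a large effect was unlikely to have been missed. The Protocol Summary also gives the tDCS-versus-sham comparison the role of a positive control, so a null result there could be misread in the same way.

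**Working it through.** The plan gives no power figure to reproduce, so the check asks what 16 per arm delivers under stated assumptions.

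**Inputs from the documents.** Three arms of 16 (Table 1 and section 11.2); AHRS immediately before the first and after the last stimulation (3.2.1, 11.1.1); mixed ANOVA, then t-tests (11.3).

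**Assumptions, none stated in the documents.** Two-sided alpha 0.05; all 48 evaluable; 'enough' means 80%; 'large' means a largest between-arm difference of 0.8 SD of AHRS change, or alternatively f = 0.40.

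**Primary test.** With two time points, the session-by-treatment interaction is a one-way ANOVA on change, F with 2 and 45 df. With SD of change set to 1, λ = 16 × Σ(μᵢ − μ̄)² and f = √(λ/48).

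- tDCS equal to tACS, means (0, 0.8, 0.8), or equal to sham, (0, 0.8, 0): Σ = 0.4267, λ = 6.83, f = 0.377, power **61.3%**.
- tDCS midway, means (0, 0.8, 0.4): Σ = 0.32, λ = 5.12, f = 0.327, power **48.6%**.
- f = 0.40: λ = 48 × 0.16 = 7.68, power **66.7%**. This corresponds to a difference of 0.85 SD, or 0.98 SD with tDCS midway.

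The first two are the best and worst patterns for three means spanning 0.8 SD. Simulation (100,000 runs) gave 61.4% and 48.6%. The difference detectable with 80% power is 0.98 SD, or 1.14 SD with tDCS midway.

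**Unpaired tACS versus sham.** Noncentral t, 30 df, noncentrality 0.8 × √(16/2) = 2.26.

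| Correction | Power at 0.8 SD | Difference for 80% power |
|---|---|---|
| None (0.05) | 59.1% | 1.02 SD |
| Bonferroni over two (0.025) | 47.1% | 1.14 SD |
| Bonferroni over three (0.0167) | 40.6% | 1.20 SD |

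**Readings more favourable to the plan.**

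1. *0.8 in raw-score SDs.* With equal variances before and after, SD of change = raw SD × √(2(1 − ρ)), so the effect on the change scale is 0.8/√(2(1 − ρ)). Omnibus power, best pattern / tDCS midway: ρ = 0.3, 47% / 36%; ρ = 0.5, 61% / 49%; ρ = 0.7, 84% / 72%; ρ = 0.8, 96% / 88%. Power reaches 80% at ρ ≈ 0.67 (0.75 if midway); for example, 0.8/√(2 × 0.331) = 0.98.
2. *Significance on either AHRS or EEG.* With 0.8 SD on both and independent outcomes, power is 1 − (1 − 0.613)² = 85% (74% if midway), and the false-positive rate is 1 − 0.95² ≈ 10%. Simulation with between-outcome correlation from 0 to 0.5 gave 78% to 85% (66% to 74% if midway), with 9% to 10% false positives.
3. *Paired t-test within one arm.* 15 df, noncentrality 0.8 × √16 = 3.2: power 85% uncorrected, 75% with Bonferroni over two, 69% over three.

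**The case against.** The strongest reply is that section 11.2 prints no number, so nothing has been miscalculated, and every percentage above rests on inputs supplied here. That is right. The defect is an unsupported assertion, and 49% to 67% is a conditional figure that should not be quoted as the trial's power.

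A second reply is that the clause is broad. It covers either active treatment and either hallucinations or biomarkers, and section 11.3 names a paired test. Some of these readings do reach 80%. This stands in part. The either-outcome reading roughly doubles the 5% false-positive rate, and it falls below 80% if tDCS is midway or the two outcomes are correlated at 0.5. The within-arm paired test does not address the between-group hypothesis of section 11.1.1.

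Third, the 49% end requires tDCS to lie exactly midway. A positive-control role fits an expected full tDCS effect (61%) better, though it does not exclude a smaller one.

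A reader might go further and infer that the power claim is false, or that 48 is too few. The documents do not support either inference. In raw-score SDs, a pre/post correlation of 0.7 gives 84% in the best pattern. The entry rule, "A stable score is defined as having less than or equal to 20% change", selects stable scorers and may favour a high correlation, but it does not fix one. Nor does a pilot framed around feasibility and preliminary efficacy (section 4) have to reach 80% power.

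**Conclusion.** The assertion of adequate power is unsupported as written. For the between-arm AHRS test it is also not met under the two conventional meanings of 'large' on the change scale: about 49% to 61% at 0.8 SD, and 67% at f = 0.40. An effect of 0.8 SD of change would be missed about 39% to 51% of the time.

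This rests on two-sided alpha 0.05, 80% as the standard and 16 evaluable per arm, which is the best case for 48 recruited. It does not extend to every reading, because the answer depends on a pre/post correlation that the plan does not state. The consequence is for how a null result is interpreted; the design and its analysis are not invalidated.

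**What to change.** Keep N = 48, the hypotheses and the analysis. Replace the power clause in section 11.2 with:

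> No formal sample size calculation was done. Assuming two-sided alpha 0.05 and 16 evaluable participants per arm, the session-by-treatment test on AHRS has 80% power for a largest between-arm difference of about 0.98 SD of change (1.14 SD if one active arm is midway), and about 49% to 61% power at 0.8 SD; a non-significant result does not exclude a large effect.

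Add the pairwise detectable difference for the Bonferroni family that the sponsor intends: 1.02 SD uncorrected, 1.14 SD over two comparisons or 1.20 SD over three. If the sponsor has a pre/post AHRS correlation, state it and give the raw-score equivalent.

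The cost is one replaced clause and a short addition. The downside is a less favourable stated sensitivity.

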### **14.3 Types of Data**

Data will be collected to determine eligibility. During the initial session, the SCID, AHRS, PANSS, CGI-S, SAS and AIMS will be administered. In order to participate in this study, the participant must have a diagnosis of schizophrenia or schizoaffective disorder, experience medication refractory auditory hallucinations, and are currently not committed in an inpatient hospital and on stable medication.

We will also be collecting data to assess cognitive abilities at the 1st day of stimulation, the 5th day of stimulation and end point (one month follow-up). The BACS will be used to assess cognition in each participant and will be used as a safety monitor and data collection tool to

monitor any changes throughout the course of the study.

The stimulation adverse effects questionnaire will be administered after each stimulation in order to monitor any side effects the participant may experience from the stimulation treatment. After the last stimulation and at the one week and one month follow-up, participants will be asked whether they believe their symptoms have improved due to treatment.

The AHRS will be our primary outcome for this study. We will administer this questionnaire at the initial session, on the 1st day of stimulation, the 5th day of stimulation, and the one week and one month follow up. As our primary outcome, the data we collect with the AHRS will be used to determine efficacy of treatment.

The PANSS, the CGI-S, the SAS and the AIMS will be used to collect additional data throughout the study. This questionnaire will also be administered on the 1st day of stimulation, the 5th day of stimulation, and the one week and one month follow up, in addition to during the initial session.

An EEG recording will be performed at the 1st day of stimulation, the 5th day of stimulation, and at the one week and one month follow-up. The data collected from the EEG recording will enable assessment of neurophysiological changes induced by stimulation.

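### The précis asks whether tACS beats sham, but section 11 reaches that comparison only as a post-hoc, Bonferroni-corrected test; make it the planned primary contrast and give the tDCS positive control a stated reading

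*Combined protocol and SAP*

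**What the plan says.** - **Protocol Summary, Précis.** The purpose is the efficacy of tACS versus sham, "with tDCS versus sham as a positive control for assay sensitivity". In the text available, that role is stated only here.
- **Section 11.1.1.** The primary null hypothesis is: "There is no difference in AHRS score immediately before first stimulation session and immediately after last stimulation session between treatment groups". It covers all three arms and names no pair and no direction.
- **Section 11.2.** Because this is a pilot, "therefore we do not calculate sample size". The section then asserts "with 16 participants in each group that we have enough power to detect significance if there is a large effect size". The effect is attributed to either active arm: "if there is a large effect size of twice daily tACS or tDCS on auditory hallucinations".
- **Section 11.3.** A mixed ANOVA (session by treatment) is followed by t-tests, paired or unpaired, "to identify the group or groups that differed". Then: "We will further control for multiple comparisons by using Bonferroni corrections". Neither the number of comparisons nor an alpha level is given.
- **Section 14.3.** For the primary outcome, "the data we collect with the AHRS will be used to determine efficacy of treatment".

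**The concern.** The question in the précis and the test in section 11 are not the same. The comparison of main interest has no protected place. It shares an error budget of unknown size with the positive control and possibly with other comparisons. A paired test within one arm, which section 11.3 permits, would not compare anything with sham.

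A positive control matters most when the test treatment looks null, and here the plan gives no operational rule. It does not say which result establishes assay sensitivity. It also does not say what is concluded about tACS if tDCS separates from sham and tACS does not, or if neither does. Section 11.2 says a pilot serves to decide whether a large trial follows, so a loosely read null could wrongly end work on tACS, and a lost comparison could leave the decision without its main evidence.

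**Working it through.** **What can be reproduced.** Only 3 × 16 = 48. The power statement in section 11.2 cannot be reproduced, because no effect size, SD, alpha or target power is given.

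**Inputs.** n = 16 per arm (section 11.2). Assumed: all 16 evaluable, two-sided tests, base alpha 0.05, and a Bonferroni family of one, two or three pairs (0.05, 0.025, 0.0167). The effect d is the between-arm difference in AHRS change divided by the SD of change. With two sessions, the session-by-treatment term is a one-way comparison of change scores, so this is the relevant scale.

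**Detectable difference.** The two-sample t-test has 30 df and noncentrality d√(n/2) = 2.828d. Solving for 80% power:

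| Family | Alpha | Detectable d | Ratio to 1.024 | n per arm to hold 1.024 SD |
|---|---|---|---|---|
| 1 | 0.05 | 1.024 | 1.00 | 16 (total 48) |
| 2 | 0.025 | 1.138 | 1.11 | 20 (total 60) |
| 3 | 0.0167 | 1.202 | 1.17 | 22 (total 66) |

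This table needs no assumed effect, SD or pre-post correlation, only the family size. With 14 evaluable per arm the detectable d becomes 1.100, 1.225 and 1.295.

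**Power at an assumed d = 0.8.** Normal approximation: 0.8 × 2.828 = 2.263. At alpha 0.05, 2.263 − 1.960 = 0.303, giving 0.62 (exact t 0.59). At 0.0167, 2.263 − 2.394 = −0.131, giving 0.45 (exact t 0.41). By simulation with both active arms at 0.8, requiring a significant three-group F-test as well as 0.05/3 gives 0.40. A single planned contrast at 0.05 with error pooled over three arms (45 df) gives 0.60.

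**Spread over assumed effects.** Exact-t power at alpha 0.05 / 0.0167 is 0.28 / 0.15 at d = 0.5, 0.59 / 0.41 at 0.8, 0.78 / 0.62 at 1.0, and 0.98 / 0.95 at 1.5.

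**Reading the positive control.** In simulated trials with equal true effects in both active arms, tDCS-sham is significant and tACS-sham is not in these shares (alpha 0.05 / 0.0167):

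- d = 0.8: 16% / 16%
- d = 1.03: 11% / 15%
- d = 1.26: 5% / 9%

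The last two effects equal 0.8 raw SD divided by √(2(1 − ρ)), with assumed pre-post correlation ρ of 0.7 and 0.8. In such trials the direct tDCS-tACS test at 0.05 is significant only 11–15% of the time. Requiring it before calling tACS inferior leaves that wrong conclusion in about 1–2% of all trials.

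**Price of that requirement.** If tACS truly has no effect, at alpha 0.05, the conclusion that tDCS is better is reached in 42% rather than 56% of trials at a tDCS effect of 0.8 SD, and in 85% rather than 89% at 1.26 SD.

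**The case against.** The strongest reply is that this is a pilot. Section 4 sets its aims as feasibility and preliminary efficacy data, and section 11.2 openly declines a sample size calculation. The post-hoc t-tests would include tDCS versus sham and tACS versus sham. The term positive control has an ordinary reading: if it fails, the trial is uninformative. Section 2.1 also cites an earlier tDCS study with a significant, lasting decrease in hallucinations. Finally, section 11.2 speaks of an effect of either active arm, so giving up a tDCS claim is a design choice.

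Much of this stands, and it rules out three stronger readings that a reader might infer.

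- *That 16 per arm is too few.* The documents do not support this. Power runs from about 0.15 to above 0.95 over the assumed effects and alphas.
- *That the positive control has no support and no test.* Section 2.1 gives a qualitative rationale, though no effect size, and section 11.3 covers the pair generically. What is missing is its designation, its alpha and a rule for reading it.
- *That the plan as written costs the equivalent of 18 participants (66 against 48).* That holds only for a family of three. The documents name no family. Adding tDCS-sham alone gives a family of two.

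Pilot status excuses the missing sample size calculation. It does not explain why the analysis is built around a different question from the one in the précis.

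**Conclusion.** The point holds as a mismatch between the stated question and the stated test, with an inexpensive improvement available. It does not show that the trial is underpowered or invalid.

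Making tACS versus sham the single planned contrast keeps the detectable difference at 1.02 SD of AHRS change. The alternative is 1.14 or 1.20 SD, an increase of 11% or 17%, if Bonferroni spans two or three pairs. At an assumed 0.8 SD, power is about 0.60 instead of 0.40. The first comparison rests on the assumed family, two-sided 0.05 and 16 evaluable per arm. The second also assumes the effect size and that the t-tests follow only a significant three-group test. The change should be made, and made before unblinding.

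**What to change.** Amend sections 11.1.1 and 11.3 together, so that hypothesis and analysis agree:

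- **Primary test.** The planned between-group contrast tACS versus sham on AHRS change, from before the first to after the last stimulation, two-sided 0.05.
- **Assay-sensitivity contrast.** tDCS versus sham on the same change, two-sided 0.05, reported separately and not used for an efficacy claim for tDCS.
- **Supportive analyses.** The three-group mixed ANOVA and the other pairwise tests, with Bonferroni applied to a listed set of secondary comparisons.
- **Reporting.** All three pairwise differences with 95% confidence intervals.
- **Reading rule.** If tACS-sham is significant, it is read on its own, whatever the tDCS result. If it is not, the trial is inconclusive on tACS, whether or not tDCS-sham is significant. The one exception is when tDCS-sham is significant and the 95% confidence interval for the direct tDCS-tACS difference excludes zero; tACS is then described as less effective than tDCS.

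In section 11.2, replace the power clause with: *16 evaluable participants per arm give 80% power (two-sided 0.05) for a difference of 1.02 SD of AHRS change.*

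**Cost.** No extra participants or visits. The trial gives up a separate tDCS efficacy claim; if one is wanted, state a family of two and 1.14 SD instead. The conclusion that tDCS is better than tACS becomes harder to reach, by the amounts shown in the working.
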